12.3.3 Adverse Events

12.3.3.1 Definitions

Adverse events will be coded per the Medical Dictionary for Regulatory Activities (MedDRA). They will be classified into predefined standard categories per chronological criteria:

- Pretreatment AEs: AEs that developed or worsened during the pretreatment phase;
- Treatment-emergent adverse events (TEAEs): AEs that occurred or worsened at any time during the on-treatment phase;
- Post-treatment AEs: AEs that occurred during the post-treatment phase after discontinuation of lens wear.

If the start date (or time) of an AE is incomplete or missing, then the AE will be considered as a TEAE unless a partial date (or time) show it as a pre- or post-treatment event.

All AEs reported in the study will be listed by subject and onset date. Nevertheless, the analyses of the AEs will focus on the treatment-emergent or post-treatment adverse events.

12.3.3.2 Treatment-emergent or Post-treatment Adverse Events

An in-text table of overview of treatment-emergent or post-treatment adverse events subjects with any treatment-emergent or post-treatment AE, subjects with any severe treatment-emergent or post-treatment AE, subjects with any treatment-emergent or post-treatment serious AE, subjects with any treatment-emergent or post-treatment AE leading to permanent treatment discontinuation, or any treatment-emergent or post-treatment AE leading to death (only if death occurred), will be produced by treatment group.

Subjects presenting with treatment-emergent or post-treatment AEs will be listed sorted by treatment group, primary system organ class (SOC), and preferred term (PT).

Treatment-emergent or post-treatment AEs will be summarized by treatment group, tabulating:

- The number and percent of subjects with at least 1 treatment-emergent or post-treatment AE within each and over all SOC(es);
- The number and percent of subjects experiencing each PT in each SOC;
- The number of occurrences of all PT(s) within each and over all SOC(es);
- The number of occurrences of each PT in each SOC.

12.3.3.3 Deaths, Serious and Other Significant Adverse Events

Any deaths and SAEs will be listed.

12.3.3.4 Adverse Events Leading to Treatment Discontinuation

Any TEAE or post-treatment AE leading to permanent treatment discontinuation will be listed.

12.4 Subject Disposition

A detailed description of subject accountability, including number of subjects randomized and receiving Test or Control product, number of subjects who did not complete the study treatment period along with the main reason for permanent treatment discontinuation, and number of subjects who requested treatment discontinuation, will be generated for all subjects.

12.5 Demographics and Baseline Characteristics

12.5.1 Subject Demographic Characteristics, Medical History and Diagnoses

Continuous variables (age) and the qualitative variables (gender, race) will be summarized by descriptive statistics for all subjects for the Safety Population. In the event that more than 10% of subjects discontinue prior to completing the study, separate summaries of demographic characteristics will be provided for the PP Population.

Medical history that is current and relevant for the past 2 years will be collected.

Demographic data will be listed by subject.

12.6 Protocol Deviations

The following protocol deviations will be classified as major deviations when reported in the case report forms.

- Ineligibility
- Non-dispensed subjects
- Misrandomization
- Dispensing or use of the incorrect lens type
- Dispensing of the incorrect lens power, defined as a discrepancy greater than 0.25D in sphere, cylinder, or spherical equivalent
- Non-compliance with the recommended wearing schedule, such as
 - wearing lenses less than 80% of the recommended time, or
 - wearing a lens for multiple days

- Use of medications that could potentially affect ocular physiology or lens performance
- Failure to comply with the procedures used to assess primary effectiveness endpoints, such as missing the assessment or failing to complete the procedure in accordance with the instructions provided by site personnel.

Additional major categories may be added prior to unmasking. Major deviations will be provided in a listing.

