- g. Discuss the diary with instructions to complete on a weekly basis. Subjects will be provided with a reminder at every visit to complete the diary to capture wear experience on a weekly basis until they exit the study.
- h. If the subject is discontinued or exited at this visit, complete the Exit Visit eCRF.
- i. Re-emphasize the exclusion criterion stating that if the subject is a female of child bearing potential and is pregnant and or breast feeding, she is ineligible to be a part of the study.

11.1.3 1-Week, 1-Month, and 3-Month Follow-up Visits

- a. If this is an Exit Visit, indicate that on the eCRF and, in addition to completing the appropriate Follow-Up Visit Form, complete the Exit Visit Form. If a subject misses the scheduled follow-up visit and cannot be seen prior to the start of the visit window for the next scheduled follow-up visit, then the visit is considered missed and it should be recorded as a missed visit in the applicable eCRF.
- b. Collect/assess all AEs, including serious or significant non-serious AEs.
- c. If the subject did not wear lenses to the visit, the subject can use a pair from the 10 lenses per eye stored in the office to complete the assessment.
- d. Collect Symptoms/Complaints information using the Symptoms/Complaints Rating Scales in [Appendix A](#) and record them in the source documentation and eCRF.
- e. Evaluate the lenses (while on eye) and record the following assessments in the source documentation and eCRF:
 - distance high contract lens VA
 - over-refraction and distance VA
 - lens wettability
 - lens centration
 - lens movement

- lens rotation
- lens deposits

For each eye, compare the high contrast distance contact lens VA from each respective / current visit (1-Week, 1-Month, 3-Month Follow-up Visits) to the high contrast distance contact lens VA obtained at the Dispensing Visit. If the VA has decreased by 10 letters (0.2 logMAR) or more, record in the subject's source document and explain.

- f. Perform a slit lamp examination (remove the lenses if the subject wore lenses to the visit) and record the following assessments in the source documentation and the eCRF. Record all slit lamp findings and, at a minimum, sketch the following in the subject's source document:
 - any ungraded finding marked as "PRESENT"
 - any new corneal scars
 - any neovascularization within the central 6 mm of the cornea
 - any corneal staining

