12.1 Determination of Sample Size

12.1.1 Primary Effectiveness Endpoints

The null hypothesis is that the difference in the proportion of subjects with both eyes "0.04 or Better" between the test group (π_T) and the control group (π_C) is less than or equal to the negative value of the non-inferiority margin ($-\delta$). The alternative hypothesis is that the difference in proportions is greater than the negative value of the non-inferiority margin.

$$H_0: \pi_T - \pi_C \leq -\delta$$

$$H_1: \pi_T - \pi_C > -\delta$$

In a previous evaluation of Biotrue ONEday for Astigmatism Soft Contact Lenses, 92.5% of subjects with baseline logMAR BSCVA of 0.04 or better achieved the primary effectiveness endpoint of this study at the follow-up visit. Consequently 92.5% is the expected percentage of subjects "0.04 or Better" in the Test and Control groups. The non-inferiority margin will be set at 10% and the lower confidence limit will be compared to -10%.

A one-sided alpha risk of 0.025 (eg, a two-sided 95% confidence interval) will be used to test the hypothesis.

When the sample size in each group is 109 subjects, a two-group large-sample normal approximation test of proportions with a one-sided 0.025 significance level will have 80% power to reject the null hypothesis that the test is inferior to the control (the difference in proportions, $\pi_T - \pi_C$, is -0.10 or less) in favor of the alternative hypothesis that the test lens is non-inferior, assuming that the expected difference in proportions is 0.000 and the proportion in the standard group is 0.925.

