12.2.2 Per Protocol Population

The PP Population will include all randomized subjects without major protocol deviations who complete the study through Visit 3 (Days 6 - 10). Major protocol deviations affecting only one eye will result in the exclusion of both eyes from eye level summaries.

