12.3.2 Primary Effectiveness Analysis

At the 1-Week Follow-up Visit, subjects with non-missing logMAR acuities 0.04 or better in both eyes will be classified as “0.04 or Better.” Subjects with at least one logMAR acuity > 0.04 at the visit will be classified as “Worse than 0.04.” Subjects with at least one missing value at the visit will not be classified and their classification value will be assigned as missing. Visual acuity of 0.04 logMAR is the acuity where an individual subject would be given credit for reading logMAR 0.0 and logMAR 0.0 is equivalent to Chinese logarithmic visual acuity chart value of 5.0.

The summaries and analyses of the primary effectiveness endpoint will be at the subject level.

Use of the ITT Population and imputation of missing values are not conservative practices in non-inferiority analyses. Consequently, the PP Population will be used for the primary analysis without imputation of missing data.

Primary Non-Inferiority Analysis with the Per Protocol Population

VA Effectiveness will be summarized categorically (0.04 or Better, Worse than 0.04) by treatment group at the 1-Week Follow-up Visit for the Per Protocol (PP) Population in a table. Missing data will not be imputed for this primary analysis of the PP Population. The denominator for percentages will be the number of non-missing values.

The difference between treatment groups (Test minus Control) in the proportion of subjects classified as “0.04 or Better” will be estimated. An asymptotic Wald non-inferiority test (without continuity correction; using the sample variance; alpha risk = 0.025) and the associated two-sided 95% confidence interval will be used to test the statistical hypothesis. The difference between treatment groups (in percentage units), the asymptotic standard error for the difference (in percentage units), the associated Z value, the p-value for the non-inferiority test, and a two-sided 95% confidence interval (in percentage units) around the difference will be presented. [REDACTED]

Sensitivity Analysis Using the ITT Population

VA Effectiveness will be summarized categorically (0.04 or Better, Worse than 0.04) by treatment group at the 1-Week follow-up visit for the ITT Population in a table. The denominator for percentages will be the number of non-missing values. Missing data will not be imputed for this categorical summary.

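### Excluding subjects for wear below 80% from the primary per-protocol analysis, even when Week-1 lens acuity was measured, can favour non-inferiority if under-wear is related to poor acuity

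*Combined protocol and SAP*

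**What the plan says.** The primary endpoint (Section 11.4.1) is the proportion of subjects with lens-corrected logMAR acuity of 0.04 or better in both eyes at the 1-Week visit. Four provisions decide who is counted.

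- **Section 12.6** lists as a major deviation, under non-compliance with the wearing schedule, "wearing lenses less than 80% of the recommended time". It attaches no reason and no time window.
- **Section 12.2.2** defines the PP Population as "all randomized subjects without major protocol deviations who complete the study through Visit 3".
- **Section 12.3.2** makes PP the primary analysis set without imputation, on the ground that "Use of the ITT Population and imputation of missing values are not conservative practices in non-inferiority analyses". An ITT analysis with a Wald 95% interval is also planned, as a sensitivity analysis.
- **Section 12.1.1** sets the decision rule: "The non-inferiority margin will be set at 10% and the lower confidence limit will be compared to -10" percent.

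Under-wearers can reach the assessment. Section 9.4 lets subjects with deviations continue unless they are at risk or must be discontinued. Section 11.1.3, step c, says that if no lenses were worn to the visit, "the subject can use a pair from the 10 lenses per eye stored in the office".

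**The concern.** Wear time is observed after randomization and the lens can influence it. Subjects are unmasked (Section 7.1), and a subject who sees poorly in the assigned lens may wear it less. If that subject attends Visit 3 and is classified as worse than 0.04, a measured failure exists and the exclusion rule deletes it.

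The plan's reason for preferring PP does not cover this case. ITT can dilute a difference between arms, but an exclusion that depends on the outcome can also shrink the difference, and then PP is the less conservative set. The shares removed need not differ between arms: the arm with more failures has more to lose, so the same share narrows the gap.

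Because the rule has no time window, under-wear in Month 2 or 3 could, as written, remove a valid Week-1 result. With about 8 failures expected per arm (109 × 0.075 = 8.2), a borderline result can turn on one or two subjects.

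**Working it through.** **Inputs from Section 12.1.1.** "A one-sided alpha risk of 0.025 (eg, a two-sided 95% confidence interval) will be used to test the hypothesis". The margin is 10 points, there are 109 evaluable subjects per arm, and the power is computed "assuming that the expected difference in proportions is 0.000 and the proportion in the standard group is 0.925". The test is the unpooled Wald test without continuity correction (Section 12.3.2).

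**The plan's own figure.** n = 2 × 0.925 × 0.075 × (1.960 + 0.842)² / 0.10² = 108.9, so 109 per arm. This reproduces the stated 80% power (80.03% by formula). 109/0.9 gives 122 per arm.

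**Assumed quantities.** The documents give no rate of under-wear and do not say how it relates to acuity. Let f be the share of acuity failures, and g the share of acuity successes, excluded for wear time, equal in both arms.

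**Formula.** For a true success rate p, the rate in PP is p(1-g) / [p(1-g) + (1-p)(1-f)]. Bias is the PP difference (Test minus Control) plus 10 points, evaluated at the null boundary, Test 82.5% and Control 92.5%. Example with f = 20%, g = 0: Test 0.825/(0.825 + 0.175 × 0.8) = 0.8549; Control 0.925/(0.925 + 0.075 × 0.8) = 0.9391; difference -8.4 points; bias +1.6.

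One-sided error is by exact enumeration of two binomials, with n per arm equal to 109 minus the rounded expected exclusions.

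| Failures removed (f) | Successes removed (g) | Bias, points | One-sided error |
|---|---|---|---|
| 0 | 0 | 0 | 0.030 |
| 10% | 0 | +0.8 | 0.043 |
| 10% | 5% | +0.4 | 0.036 |
| 10% | 10% | 0 | 0.028 |
| 20% | 0 | +1.6 | 0.071 |
| 20% | 5% | +1.2 | 0.058 |
| 20% | 10% | +0.9 | 0.049 |

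The 0.030 in the first row is the ordinary excess of the Wald test over 0.025 and has nothing to do with the exclusion.

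**Reversal.** If 25% of Control failures and nothing else are removed, the PP difference is -11.8 points and the error falls to about 0.011. The bias then runs against Test.

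**A borderline result in counts.** Control 101/109 throughout unless stated:

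- Test 98/109: lower limit -10.23%, not non-inferior.
- One Test failure removed (98/108): -9.26%, non-inferior.
- One failure removed from each arm (98/108 v 101/108): -9.95%, barely non-inferior.
- One Control failure removed (98/109 v 101/108): -10.93%, not non-inferior.

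The example shows sensitivity near the boundary and does not predict a direction.

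**The case against.** A reader might infer that the rule necessarily deletes lens failures and so favours Test. The documents do not support that. The endpoint is acuity alone: an uncomfortable under-wearer who reaches 0.04 or better in both eyes is a success, and dropping that subject lowers the arm's rate. If wear is unrelated to acuity the bias is nil, and if mainly Control failures go it reverses. This stands, and the point is conditional for that reason.

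Nor do all under-wearers stay to be measured. Section 8.4.1 makes inability to maintain the wearing schedule a reason for mandatory discontinuation, and Section 8.4.2 allows discontinuation for unacceptable lens acuity or fit. Fit is screened (Section 11.1.1) and lens acuity is checked at dispensing (Section 11.1.2), which limits vision-driven under-wear by Days 6-10. How many under-wearers reach Visit 3 is unknown. This limits the size but does not remove the mechanism.

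A minimum-wear rule is not arbitrary. In Appendix C, the Test guide describes variable vision during adaptation, generally gone within one week, and asks for at least 4 continuous hours of wear before follow-up; the Control guide prefers six hours. These statements concern adaptation and wear before a follow-up visit. They do not justify a threshold without a time window that can act on wear after Week 1.

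A reader might also infer that ITT has no part in the decision. Only the visible text can be judged: part of Section 12.3.2 is redacted after the primary test, and the ITT interval is planned, so a conflict with PP would be seen. In the visible text, ITT is a sensitivity analysis and the comparison with -10% is tied to the primary analysis. The best-case, worst-case and tipping-point analyses address missing data, not measured results excluded from PP. The recommended schedule itself may be in Appendix B, which was not available for review, so its absence is not held against the plan.

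**Conclusion.** The point holds in conditional form. Sections 12.6, 12.2.2 and 12.3.2 together let a measured Week-1 result leave the primary analysis because of wear time, for any cause and at any time in the study. This can favour non-inferiority when under-wear is related to poor lens acuity, in Test or in both arms alike.

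Over the illustrated range (10-20% of failures and 0-10% of successes removed, equally in both arms, true difference -10 points), the bias is 0 to +1.6 points and the one-sided error about 0.028 to 0.071. Those shares are assumptions. The planned ITT analysis keeps these subjects and would show a discrepancy, but the visible text does not say what follows if it disagrees with PP. The change is inexpensive and should be made before unmasking.

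**What to change.** 1. **Sections 12.2.2 and 12.6.** State that a subject with lens acuity measured in both eyes at Visit 3 is not excluded from the primary PP analysis for wear time alone, whatever the reason for under-wear, and that under-wear after Visit 3 never excludes. The rule should not depend on the stated reason: unmasked subjects would give it around the time acuity is measured, so selecting on it would itself be related to outcome. The other major deviations are unaffected.
2. **Section 12.3.2.** Declare non-inferiority only if the lower 95% limit is above -10% in both the PP analysis and the already planned ITT analysis.

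**Cost.** Some low-wear subjects enter the primary set. Keeping them needs no larger sample, since 109 per arm still gives 80% power for PP alone. Requiring both analyses lowers power: with 109 PP subjects per arm nested in 122 ITT subjects per arm, all at 92.5%, simulation (400,000 trials) gives 80.3% for PP, 84.0% for ITT and 78.4% for both. The plan should state this joint figure of about 78% in place of 80%. No added enrolment is proposed.

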12.7 Compliance

Subject compliance will be measured by reviewing diary entries and questioning the subject at each visit.

12.8 Interim Analyses

Not applicable

12.9 Additional Statistical Considerations

12.9.1 Prior/Concomitant Medication/Therapy

Medications will be classified by the latest version of the WHO-DDE dictionary.

13 Quality Control and Quality Assurance

13.1 Study Monitoring

Bausch + Lomb representatives must be allowed to visit all study site locations to assess the data, quality, and study integrity in a manner consistent with applicable health authority regulations and the procedures adopted by Bausch + Lomb.

Prior to the start of the study, member(s) of Bausch + Lomb (or designees) will review the protocol, eCRF, regulatory obligations, and other material or equipment relevant to the conduct of the study with the Investigator/Sub-Investigator and relevant study site personnel.

Monitoring visits and telephone consultations will occur as necessary, or per the Monitoring Plan, during the course of the investigation [REDACTED]

During the course of the study, if the Sponsor determines that an Investigator is not compliant with the protocol and/or applicable regulatory requirements, the Sponsor will take action to secure compliance. In addition, the Sponsor may terminate the Investigator's participation in the study if appropriate, or if the Investigator remains non-compliant despite the Sponsor's actions.

13.2 Audits and Inspections

Audits of clinical research activities in accordance with the Sponsor's internal Standard Operating Procedures to evaluate compliance with the principles of GCP may take place. A regulatory authority may also wish to conduct an inspection (during the study or after its completion). If an inspection is requested by a regulatory authority and/or IRB, the Investigator must inform the Sponsor immediately that this request has been made.

13.3 Data Quality Assurance

13.3.1 Use and Completion of Case Report Forms (CRFs) and Additional Request

Subject data required by this protocol are to be transferred from the source to the eCRFs. The Investigator and his/her study site personnel will be responsible for completing the eCRFs. The Investigator is required to verify that all of the requested information is accurately recorded on the eCRFs by providing an electronic signature. All information requested on the eCRFs needs to be supplied, including subject identification and initials, date(s), assessment values, etc., and any omission or discrepancy will require explanation. All information on eCRFs must be traceable to source documents.

The study monitor will be responsible for reviewing and verifying the data recorded on the eCRFs per the study Monitoring Plan, utilizing the original source documentation and will query discrepant findings. The Investigator and study site personnel will be responsible for answering all queries.

A copy of the eCRFs will be retained by the Investigator at the conclusion of the study, who must ensure that they are stored in a secure place.

14 Ethics and Administrative Issues

14.1 Ethical Conduct of the Study

This clinical trial will be conducted in accordance with the principles laid down by the World Medical Association – General Assembly (Helsinki, and all applicable amendments) laid down by the World Medical Association general assemblies, and the International Conference on Harmonisation (ICH) guidelines for GCP. This clinical trial will be conducted with all international guidelines, national laws and regulations of the country(ies) in which the clinical trial is performed, as well as any applicable guidelines.

14.2 Ethics Review

As required by local regulation, the Investigator and/or the Sponsor must submit this clinical trial protocol to the appropriate IRB/IEC, and is required to forward to the respective other party a copy of the written and dated approval/favorable opinion of the IRB/IEC (signed by the chairman with IRB/IEC composition).

The clinical trial (study number, clinical trial protocol title and version number), the documents reviewed (clinical trial protocol, ICF, Investigator's Brochure, Investigator's curricula vitae, etc.) and the date of the review should be clearly stated on the written IRB/IEC approval/favorable opinion.

Investigational medicinal product will not be released at the study site and the Investigator will not start the study before the written and dated approval is received by the Investigator and the Sponsor.

During the clinical trial, any amendment or modification to the clinical trial protocol should be submitted to the IRB/IEC before implementation, unless the change is necessary to eliminate an immediate hazard to the subjects, in which case the IRB/IEC should be informed as soon as possible. It should also be informed of any event likely to affect the safety of subjects or the continued conduct of the clinical trial, in particular any change in safety. All updates to the Investigator's Brochure will be sent to the IRB/IEC.

A progress report is sent to the IRB/IEC at least annually and a summary of the trial's outcome at the end of the clinical trial.

